## 1 Protocol Summary

### 1.1 Synopsis

**Protocol Title:** Evaluation of atomoxetine and oxybutynin for obstructive sleep apnea in children with Down syndrome

Phase 2

**Sponsor:** National Institutes of Health

**Rationale:**

Atomoxetine 80 mg/oxybutynin 5 mg (ato-oxy) has been shown support for efficacy and safety in adults without Down syndrome (DS) with obstructive sleep apnea (OSA). Children with DS have a high prevalence of OSA, and there most children with DS and OSA are not effectively treated for their OSA. Given that airway hypotonia is a cardinal feature of OSA in children with DS, and that ato-oxy specifically targets airway hypotonia, ato-oxy may be particularly effective for OSA treatment in children with DS. This Phase 2 clinical study will examine the efficacy of ato-oxy in children with DS and OSA. Overall, the study is expected to provide evidence of ato-oxy efficacy in OSA treatment as well as potential improvement in health-related quality of life.

Objectives	Endpoints
Primary To evaluate the short-term efficacy of high dose ato-oxy vs. low dose ato-oxy for treatment of OSA in children with DS	Primary Efficacy Endpoint 
 
Change in obstructive AHI from baseline (high dose ato-oxy vs. low dose ato-oxy).
 

Secondary To assess the effects of high dose ato-oxy vs. low dose ato-oxy on OSA-related health-related quality of life and sleep quality in children with DS	Secondary Efficacy Endpoints High dose ato-oxy vs low dose ato-oxy, in order: 
 
Change in OSA-18 score from baseline
 
Change in arousal index from baseline
 

Tertiary/Exploratory	Unranked Efficacy Endpoints High dose ato-oxy vs low dose ato-oxy: 
 
Change in PedsQL total score from baseline
 
Change in Caregiver Global Impression of Change from baseline
 
Change in N1 sleep (%) from baseline
 
Change in REM sleep (%) from baseline
 
Change in N3 sleep (%) from baseline
 
Vineland 3 adaptive behavior composite scale
 
Conners-3 ADHD Index
 

Abbreviations: AHI = apnea-hypopnea index; Ato-oxy = atomoxetine and oxybutynin; DS= Down syndrome; OSA = obstructive sleep apnea

**Overall Design:**

This is a randomized, double blind, cross-over study of the combination of atomoxetine and oxybutynin (ato-oxy) in children with DS and OSA documented by polysomnography (PSG). Participants will receive high dose ato-oxy for four weeks as well as low dose ato-oxy for four weeks in random order. During the high dose ato-oxy period, participants will take 5 mg oxybutynin and 0.5mg/kg/day (max 40 mg) atomoxetine nightly for one week. Atomoxetine dose will then be increased to 1.2 mg/kg/day (max 80 mg). During the low dose ato-oxy period, participants will take 5 mg oxybutynin and 0.5mg/kg/day (max 40 mg) atomoxetine. Dosing of the study treatment will occur approximately 30 minutes prior to bedtime. Participants who withdraw from the study will not be replaced.

Study participants will undergo eligibility screening that will include an initial screening to determine whether non- PSG enrollment criteria are met, followed by a 1-night in-lab PSG and health-related quality of life assessment for participants who qualify based on non-PSG criteria. For participants who are eligible and enroll in the study, the screening PSG night will serve as the baseline measure for apnea-hypopnea index (AHI) and other PSG endpoints. On the final night of dosing for both high dose ato-oxy and low-dose ato-oxy, participants will return for inpatient PSG and health-related quality of life assessment. The primary efficacy endpoint is the change in obstructive AHI from baseline (high dose ato-oxy vs. low dose ato-oxy).

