**Treatment Groups and Duration:**

All participants will receive both high dose ato-oxy and low dose ato-oxy in random order.

[figure not shown]
The overall study duration will be up to 15 weeks, as follows:

- Up to 28 days for screening and baseline PSG;
- 28 nights of high dose ato-oxy (with PSG and health-related quality of life assessment on the last night of high dose ato-oxy)

- 14-21 days of wash-out period between high dose ato-oxy and low dose ato-oxy periods
- 28 nights of low dose ato-oxy (with PSG and health-related quality of life assessment on the last night of low dose ato-oxy)

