### 1.3 Schedule of Activities (SoA)

**Table 1** Schedule of Activities

	Visit 1 	Post-visit 1	Phone call 1	Phone Call 2	Phone Call 3	Visit 2 	Post-visit 2 	Phone call 4	Phone Call 5	Phone Call 6	Visit 3 
Trial Day (Visit Window)	-28 to -1	1	7±4	14±4	21±4	28±4	42	49±4	56±4	63±4	70±4
Inclusion/Exclusion Criteria	X										
Demography	X										
Informed Consent 	X										
Vital Signs 	X					X					X
Polysomnography	X					X					X
Quality of Life and behavioral assessments 	X					X					X
Randomization		X									
Drug dispensed 		X					X				
Adverse event screening			X	X	X	X		X	X	X	X

Prior/concomitant medication monitoring	X		X	X	X	X		X	X	X	X
Counting of returned study drug						X					X
LENA language evaluation 	X					X					X

- 1 Pre-screening including verification of inclusion/exclusion criteria, demography as well as informed consent may be performed prior to visit 1 at investigator/participant preference, including at the study recruitment site. Baseline polysomnography may occur up to one month prior to initiation of study drug, but preferably within one week. This will be done to assist with scheduling of on-therapy PSG, which should occur on the last night of therapy. This will additionally allow participants to spread PSGs over a longer time period if desired.
- 2 Final study eligibility is determined after the baseline PSG exam, based on PSG and non-PSG findings, and enrolled participants are randomized and dispensed the study drug.
- 3 Polysomnography and health-related quality of life assessment should occur on the last day of therapy, but may vary by 4 days if needed due to extenuating circumstances. Participants must bring and consume study medication in the sleep lab on polysomnography nights.
- 4 Drug washout period will be 14 days (preferable and minimum), but may be extended to no more than 21 days to assist with scheduling of the second on-therapy PSG, which should occur on the last night of therapy.
- 5 No trial-related assessment is to be carried out before the participant has signed the ICF. Any participant who provides informed consent will have a screening number assigned.

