## 4.2 Scientific Rationale for Study Design

Atomoxetine 80 mg/oxybutynin 5 mg (ato-oxy) has been shown support for efficacy and safety in adults without Down syndrome (DS) with obstructive sleep apnea (OSA). Children with DS have a high prevalence of OSA, and most children with DS and OSA are not effectively treated for their OSA. Given that airway hypotonia is a cardinal feature of OSA in children with DS, and that ato-oxy specifically targets airway hypotonia, ato-oxy may be particularly effective for OSA treatment in children with DS. This Phase 2 clinical study will examine the efficacy of ato-oxy in children with DS and OSA. Overall, the study is expected to provide evidence of ato-oxy efficacy in OSA treatment as well as potential improvement in health-related quality of life.

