**Exclusion Criteria based on baseline polysomnography (prior to randomization)**

1. Hypoxemia independent of respiratory events on polysomnography ( $\geq 5$  minutes with oxygen saturation <90%)

2. Presence of central sleep apnea on polysomnography (central AHI  $\geq 5$ )

3. Absence of OSA defined as total AHI <5

[figure not shown]
Children with or without history of prior adenotonsillectomy will be enrolled as long as they have current OSA (defined as AHI  $>5$ ) on baseline polysomnography. Children who are initially excluded due to tonsillar hypertrophy will be eligible to participate in the study if they have persistent OSA after adenotonsillectomy. Additionally, children will be eligible regardless of body mass index (BMI), as the prior study of ato-oxy in adults included participants with

significant obesity, and ato-oxy was demonstrated to be effective in adults with a BMI as high as 40 (Taranto-Montemurro, Messineo et al. 2018).

Pediatric OSA is defined in the International Classification of Sleep Disorders (3rd edition) by an obstructive AHI  $\geq 1$ . While we considered using this as our inclusion criteria to maximize generalizability to all children with OSA, we decided against this approach for several reasons.

First, half of our study population will be adolescents, and based on American Academy of Sleep Medicine guidance in the current polysomnography scoring manual, use of the adult definition of OSA (total AHI  $\geq 5$ ) may be more appropriate in adolescents.

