Second, the prior adult study of ato-oxy as well as the ongoing study of hypoglossal nerve stimulation in children with Down Syndrome both required a total AHI  $> 10$  to enroll in the study. The preliminary data published to date from the ongoing study of hypoglossal nerve stimulation does not show any evidence of a floor effect in the outcome of AHI % reduction (Caloway, Diercks et al. 2020), which may be due to their selected AHI threshold that includes only children with moderate-severe OSA. However, in the study, despite an 85% reduction in AHI as well as significant improvement in OSA-related quality of life, only a single participant (5%) had an AHI  $< 1$  after intervention. An apparent floor effect did appear to be present in the prior study of ato-oxy in adults, which did include participants with mild OSA (defined by a total AHI  $> 5$  and  $< 15$  in adults) (Taranto-Montemurro, Messineo et al. 2018) as visually apparent from their Figure 2b (below).

Given these prior findings, we were concerned that the use of an obstructive AHI  $\geq 1$  as an inclusion criterium would potentially create a floor effect, where we would see no overall significant improvement due to a lack of improvement in participants with mild OSA, even though participants with moderate to severe OSA may show improvement.

Based on this rationale, we selected total AHI  $\geq 5$  as the threshold for progressing to drug randomization in the study. This threshold is likely more

appropriate for many adolescent participants and will reduce the likelihood of a floor effect in the current study. If the current study does show a significant improvement in AHI, a future study would be needed to evaluate the efficacy of ato-oxy in children with mild OSA.

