## 9.4 Primary and Secondary Analyses

Below is a summary of planned statistical analyses of the primary, secondary and exploratory endpoints.

For the primary outcome, each participant's changes in obstructive AHI from baseline will be derived for both periods (high dose ato-oxy and low dose ato-oxy). To account for the features of a 2 by 2 crossover design, a linear mixed effects model with a subject random effect and a dose sequence indicator (e.g. high dose ato-oxy → low dose ato-oxy sequence indicator), a period indicator (e.g. 2nd period indicator) and a high dose ato-oxy dose indicator as the covariates will be fitted to the changes in obstructive AHI. This model will allow us to evaluate the effect of high dose ato-oxy on changes in obstructive AHI compared with the effect of low dose ato-oxy (primary analysis) while accounting for the potential carry-over, period and subject effects. In addition, it will also allow us to evaluate whether the overall mean change from baseline is different from zero by testing the intercept of the model and whether the carry-over or period effect exists by testing the regression coefficient estimate for the treatment sequence indicator and the period indicator, respectively (secondary analysis). Prior research has shown that obstructive AHI is likely to be not normally distributed. Therefore, a suitable transformation will be sought and applied to changes in AHI before the mixed effects model is fitted if necessary.

For health-related quality of life aims, a similar statistical analysis plan will be implemented. Specifically, a linear mixed effects model with a subject random effect and a treatment sequence indicator (e.g. high dose ato-oxy → low dose ato-oxy sequence indicator), a period indicator (e.g. 2nd period indicator) and a high dose ato-oxy dose indicator as the covariates will be fitted to the changes in OSA-18 (secondary outcome), PedsQL and Caregiver global impression of change (exploratory outcomes), respectively. If necessary, a suitable transformation will be sought and applied to changes in these measures, although prior research has shown that OSA-18 is normally distributed (Jung, Kim et al. 2011).

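### The screening night that admits a child is also the only untreated baseline, so the secondary test of mean change against zero is not a test of no drug effect

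*Combined protocol and SAP*

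**What the plan says.** Section 1.1 (Overall Design), repeated in 4.1, makes one night the reference for every change: "the screening PSG night will serve as the baseline measure for apnea-hypopnea index (AHI) and other PSG endpoints". Section 5.2 applies the entry gate to that same night. The exclusion reads "Absence of OSA defined as total AHI <5", and the rationale calls a total AHI of at least 5 the "threshold for progressing to drug randomization in the study". (Elsewhere in 5.2 and in 6.3 the cut-off is written as above 5. Those places should be reconciled, but nothing here depends on it.)

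There is no placebo period: "All participants will receive both high dose ato-oxy and low dose ato-oxy in random order". The Schedule of Activities (1.3) has PSG at Visits 1, 2 and 3 only. For Visits 2 and 3, "Polysomnography and health-related quality of life assessment should occur on the last day of therapy", so both are on drug. No PSG is scheduled at the end of washout, and 8.1.2 allows a baseline repeat only when the first recording is technically inadequate.

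Section 9.4 says the mixed model will also be used to "evaluate whether the overall mean change from baseline is different from zero by testing the intercept of the model", labelled secondary analysis. Sections 1.1, 2.1 and 4.2 state that "the study is expected to provide evidence of ato-oxy efficacy in OSA treatment". Regression to the mean is not mentioned, and no limit is placed on how the change from baseline may be read.

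**The concern.** AHI varies from night to night. Children kept because one night's value was high enough will, on average, score lower on a later night even if nothing is done to them. When the selecting night is also the baseline, that drop goes straight into the change score. A mean change of zero is therefore not what one expects under no drug effect, and rejecting it does not show that the drug worked. First-night, expectation and other time effects enter the same estimate, with no untreated or placebo night to separate them.

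The exposed case is a plausible one: the two doses do not differ, but both fall from baseline. The primary result is then null and the only positive finding is the uncontrolled one, in a document whose rationale expects evidence of efficacy. How that finding may be read should be settled beforehand.

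**Working it through.** **The plan's own figure.** Section 9.2 gives 12 per sequence, an effect of 1.20 SD and two-sided alpha 0.05. The noncentrality is 1.20 × √(12/2) = 2.94 and the critical t on 22 df is 2.07, so power is 0.802, as stated. Recruitment is 24/0.9 = 26.7, rounded to 27. This sizing concerns high versus low dose only; it says nothing about the test against zero.

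**Why the primary contrast is safe.** Within a child, (high − baseline) − (low − baseline) = high − low. The baseline cancels.

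**What the intercept estimates.** Section 9.4 describes 0/1 indicators for sequence (high→low), second period and high dose. The four cell means are:
- high→low, period 1: intercept + sequence + high
- high→low, period 2: intercept + sequence + period
- low→high, period 1: intercept
- low→high, period 2: intercept + period + high

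So the intercept is the low-dose, first-period mean change in one sequence of about 12 children. The overall mean change is intercept + ½(sequence + period + high).

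**Size of the spurious fall.** Neither the AHI distribution in screened children nor its night-to-night reliability is given. Assumed: log AHI normal with total SD 1.0; screened median m = 5, 8 or 12; correlation r between nights (log scale) = 0.6 to 0.9; admission at AHI ≥ 5; total and obstructive AHI treated as one measure; no drug effect. With z = ln(5/m),

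mean fall = m·e^0.5 · [Φ(1 − z) − Φ(r − z)] / Φ(−z)

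- Largest, m = 5, r = 0.6: z = 0; 8.244 × (0.8413 − 0.7257)/0.5 = 1.91 events/h.
- Smallest, m = 12, r = 0.9: z = −0.875; 19.78 × (0.9696 − 0.9621)/0.8093 = 0.18 events/h.

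On the log scale the mean fall is (1 − r)·φ(z)/Φ(−z). This runs from 0.1 × 0.2719/0.8093 = 0.034 (3%) to 0.4 × 0.3989/0.5 = 0.319 (27%).

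**False improvement rate.** Trials of 24 such children were simulated with two drug-free later nights, and the overall mean change was tested one-sided at a nominal 2.5%:

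| Screened median | Fall, events/h (r = 0.9 to 0.6) | Rate, raw change | Rate, log ratio |
|---|---|---|---|
| 5 | 0.42 to 1.91 | 4% to 12% | 16% to 57% |
| 8 | 0.28 to 1.39 | 3% to 5% | 10% to 28% |
| 12 | 0.18 to 0.97 | about 2% | 6% to 13% |

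For the intercept as literally coded, the rates are about 2% to 6% (raw) and 4% to 24% (log ratio). The high-versus-low contrast kept a mean difference of about zero and a two-sided rejection rate of about 4% to 5%.

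**Wider inputs** (log SD 0.8 to 1.0, r up to 0.95). At a screened median of 3, where only 26% to 30% of screened children would pass the gate, the raw fall reaches 2.5 events/h and two-sided rejection reaches 52% (nominal 5%). At a median of 20 rejection is 3% to 5%.

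**The case against.** The best defence is that the plan never calls the test against zero an efficacy test. Every objective and efficacy comparison in sections 1.1 and 3, the only null hypothesis (9.1) and the sizing (9.2) are high versus low dose. The intercept test stands beside the period and carry-over tests, is not a listed endpoint and has no decision rule. A reader might infer that the trial's efficacy claim rests on the uncontrolled change, or that the plan would read any fall as efficacy. The documents do not support that. The efficacy sentence is an expectation in the rationale, and a positive randomised contrast would itself be evidence of drug activity.

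Three points on size also stand. The large rates belong to a log-ratio analysis. Section 9.4 speaks only of transforming the changes, if necessary, and changes can be negative, so their log is not available; quoting 57% as the error rate of the planned test would be wrong. Selection is on total AHI and the endpoint is obstructive AHI, so a correlation below 1 weakens the effect, though it does not remove it. And the adult median change of −15.9 quoted in 9.2 is far larger than any artefact above, so a fall of that order could not be selection alone. Without a control it still could not be separated from time and expectation effects.

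None of this makes zero the right reference value for no drug effect, and 9.4 leaves the test unqualified.

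**Conclusion.** The point holds as one of interpretation. The secondary test of mean change from baseline is not a test of no drug effect, because the admitting night is the only untreated measurement. The direction of the bias follows from the design whenever AHI varies between nights. The size cannot be computed from the documents. Under the main assumptions the fall is about 0.2 to 1.9 events/h, with a raw-scale false-improvement rate ranging from no inflation (screened median 12) to about 12% (screened median 5, r = 0.6). Higher rates need an analysis that 9.4 does not specify. Separately, with the 0/1 indicators described, the intercept is one sequence-period cell mean and not the overall mean change that 9.4 says it tests.

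A reader might go on to infer that the primary comparison is biased. It is not: the shared baseline cancels, and a high-versus-low difference remains valid evidence of a dose effect.

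**What to change.** In 9.4, replace the intercept test against zero with a descriptive estimate and confidence interval of the overall mean change, obtained by centred coding or as a least-squares mean. Label it uncontrolled and subject to regression to the mean. State in 9.4, and in the efficacy sentence of 1.1, 2.1 and 4.2, that the confirmatory conclusion is limited to high versus low dose.

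I would not try to subtract an expected selection effect using the model's within-child variance. That residual comes from two on-drug nights, includes variation in dose response, and leaves out the baseline error, which is shared by both changes and absorbed into the subject effect. It does not estimate untreated night-to-night variance.

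The cost is wording in four sections, with no extra PSG, no extra participants and no change to the primary analysis. The downside is a less favourable claim from the uncontrolled change.

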**Number of Participants:**

Approximately 27 participants will be randomized to study treatment.

**Treatment Groups and Duration:**

All participants will receive both high dose ato-oxy and low dose ato-oxy in random order.

[figure not shown]
The overall study duration will be up to 15 weeks, as follows:

- Up to 28 days for screening and baseline PSG;
- 28 nights of high dose ato-oxy (with PSG and health-related quality of life assessment on the last night of high dose ato-oxy)

- 14-21 days of wash-out period between high dose ato-oxy and low dose ato-oxy periods
- 28 nights of low dose ato-oxy (with PSG and health-related quality of life assessment on the last night of low dose ato-oxy)

## 1.2 Schema

## Figure 1 Study Design Schema

Participants will be randomized to either high dose ato-oxy or low dose ato-oxy at baseline. Polysomnography (PSG) and health-related quality of life (HR-QOL) assessment will be performed after four weeks of treatment. Participants will then take no drug for two weeks, then take the alternate treatment for four weeks with repeat PSG and HR-QOL assessment at the end of therapy.

### 1.3 Schedule of Activities (SoA)

**Table 1** Schedule of Activities

	Visit 1 	Post-visit 1	Phone call 1	Phone Call 2	Phone Call 3	Visit 2 	Post-visit 2 	Phone call 4	Phone Call 5	Phone Call 6	Visit 3 
Trial Day (Visit Window)	-28 to -1	1	7±4	14±4	21±4	28±4	42	49±4	56±4	63±4	70±4
Inclusion/Exclusion Criteria	X										
Demography	X										
Informed Consent 	X										
Vital Signs 	X					X					X
Polysomnography	X					X					X
Quality of Life and behavioral assessments 	X					X					X
Randomization		X									
Drug dispensed 		X					X				
Adverse event screening			X	X	X	X		X	X	X	X

Prior/concomitant medication monitoring	X		X	X	X	X		X	X	X	X
Counting of returned study drug						X					X
LENA language evaluation 	X					X					X

- 1 Pre-screening including verification of inclusion/exclusion criteria, demography as well as informed consent may be performed prior to visit 1 at investigator/participant preference, including at the study recruitment site. Baseline polysomnography may occur up to one month prior to initiation of study drug, but preferably within one week. This will be done to assist with scheduling of on-therapy PSG, which should occur on the last night of therapy. This will additionally allow participants to spread PSGs over a longer time period if desired.
- 2 Final study eligibility is determined after the baseline PSG exam, based on PSG and non-PSG findings, and enrolled participants are randomized and dispensed the study drug.
- 3 Polysomnography and health-related quality of life assessment should occur on the last day of therapy, but may vary by 4 days if needed due to extenuating circumstances. Participants must bring and consume study medication in the sleep lab on polysomnography nights.
- 4 Drug washout period will be 14 days (preferable and minimum), but may be extended to no more than 21 days to assist with scheduling of the second on-therapy PSG, which should occur on the last night of therapy.
- 5 No trial-related assessment is to be carried out before the participant has signed the ICF. Any participant who provides informed consent will have a screening number assigned.
- 6 Vital signs include the following: seated blood pressure, pulse, Participants who experience systolic blood pressure  $\geq 140$ , or diastolic blood pressure  $\geq 90$ , or heart rate  $\geq 130$  beats per minute will be further evaluated.
- 7 Quality of life assessment will include completion of the OSA-18, Peds-QL and caregiver global impression of change. Behavioral assessments will include the Conners-3 and Vineland 3rd edition.
- 8 Daily bedtime dosing continues through the next PSG visit (for 28 days of therapy). The final night of study treatment dosing is PSG night.
- 9 Language assessment using the LENA device may take place at any point in the baseline period prior to drug administration (preferably within the week preceding baseline polysomnography, and will be repeated at any point within the last week of each drug regimen (prior to polysomnography)

